
	
The study is conducted to determine whether the nGVS alters somatosensory perception (i.e., if receiving galvanic stimulation impacts on the individual's ability to perceive sensory stimuli on the foot), the effects of nGVS on the true positive rate (TPR) for sensory perception will be compared with sham stimulation. In addition to measuring sensory perception, this study will assess if the change in somatosensory perception could have impact on balance outcomes i.e., COP sway length on force plates through dual task paradigm approach where participant is attending to somatosensory task while maintaining balance on the force plates.
 
The findings from this study will be used to better understand any somatosensory enhancement induced by nGVS in older adults. It is assumed that this proposed study will help to give a detailed view of whether the vestibular system can influence processing within the somatosensory pathway which is important for human balance and if the change in somatosensory perception could enhance COP sway length through dual task paradigm. This research will help to expand our understanding of the links between the vestibular system and the somatosensory system. It is hoped that future research will develop a nGVS intervention capable of improving balance and preventing falls in older adults.

Aims and Objectives:	
Primary Aim: To determine whether a single session of nGVS, compared with sham stimulation, alters sensory perception of a tactile stimulus measured FOLLOWING the intervention in healthy older adults.

	
Secondary objectives:
 
 1) To determine whether nGVS, compared with sham stimulation, alters sensory perception of a tactile stimulus measured DURING the intervention in healthy older adults. 2) To determine whether change in sensory perception alters COP sway length during dual task paradigm.
Study Design:	Repeated-measures crossover design
Number of Sessions:	Two
Study Population:	27 healthy older adults, ≥ 65 years to be recruited from the community on first come first served based.
Recruitment	
 • AUT gym through Never too old group • Participants from other related studies who have given consent to contact them for the future studies

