A meta-analysis of nGVS studies and the effect on balance showed no impact of nGVS on balance in adults ≥ 40 years as compared to ≤ 40 years. In the literature to quantify balance or the ability to maintain an upright posture, many variables are used for older population. The Centre of pressure (COP) sway length is one of them i.e., length of path travelled by COP. The increased COP sway length is considered as predictor of falls in standing (Howcroft et al., 2017), however, the normative quite standing cannot test older person's prediction to falls and is not considered as the appropriate measure for balance. It is important to embrace the person for spontaneous sway which could be either done by eyes closed or through narrow base of support (BOS) (Mancini & Horak, 2010).

Previously, a study was conducted to investigate the effect of nGVS on somatosensory perception in on young healthy adults (18-45 years); this showed a significant effect on the somatosensory perception of tactile stimuli to the foot from pre to post intervention. A study conducted by Johnson & Charlotte (2020) showed the touch thresholds could be a significant predictors of balance performance.

On the other hand, for maintaining balance, cognition has emerged as an important factor in older population. To evaluate the interaction between cognition and mobility, the dual-task paradigm is an accepted way in clinical practice where a person is observed during the balance task while they perform another task (Muir-Hunter et al., 2016).

Therefore, through all these findings, we want to conduct a new study investigating the effect of nGVS on the somatosensory perception of tactile stimuli in older adults aged ≥ 65 years. The study will involve participants with ≥ 65 years of age as 65 years is defined the age for older adults.

The study is conducted to determine whether the nGVS alters somatosensory perception (i.e., if receiving galvanic stimulation impacts on the individual's ability to perceive sensory stimuli on the foot), the effects of nGVS on the true positive rate (TPR) for sensory perception will be compared with sham stimulation. In addition to measuring sensory perception, this study will assess if the change in somatosensory perception could have impact on balance outcomes i.e., COP sway length on force plates through dual task paradigm approach where participant is attending to somatosensory task while maintaining balance on the force plates.

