Therefore, the primary aim of the study is to determine whether a single session of nGVS, compared with sham stimulation, alters sensory perception of a tactile stimulus measured FOLLOWING the intervention in healthy older adults. The secondary objectives are: 1) To determine whether nGVS, compared with sham stimulation, alters sensory perception of a tactile stimulus measured DURING the intervention in healthy older adults.; 2) To determine whether change in sensory perception alters COP sway length during dual task paradigm.

The findings from this study will be used to better understand any somatosensory enhancement induced by nGVS in older adults. It is assumed that this proposed study will help to give a detailed view of whether the vestibular system can influence processing within the somatosensory pathway which is important for human balance and change in somatosensory perception could enhance COP sway length through dual task paradigm. This research will help to expand our understanding of the links between the vestibular system and the somatosensory system. It is hoped that future research will develop a nGVS intervention capable of improving balance and preventing falls in older adults

3. Research Question

Research question 1: What are the effects of a single session of nGVS compared to sham stimulation on sensory perception of tactile stimuli in older adults post intervention?

Research question 2: What are the effects of nGVS on sensory perception of tactile stimulus in older adults during stimulation?

Research question 3: Does the change in sensory perception alters the COP sway length (total excursion) in healthy older adults during dual task paradigm?

4. Study Design

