5.3 EXCLUSION CRITERIA

- Diagnosed vestibular disorder or active BPPV
- Fallen more than twice in the past 6 months (Gaebler et al, 1993)
- Any diagnosed neurological impairment
- Medical conditions that are contraindicated with nGVS such as implants in head, neck, ankle or right foot, epilepsy, cardiac arrhythmias, unexplained recurring headaches, diabetic neuropathy (Thakral et al., 2013).
- Medical conditions that are cautioned with electrical peripheral stimulation of the foot such as metal implants in the area, skin lesions (Kuzyk & Schemitsch, 2009)
- Medical conditions that might affect the testing such as such as speech dysfunction, cognitive impairment
- Any allergic skin reaction to sticking plasters as a similar substance is used in the foot electrodes and to fix the nGVS electrodes

5.4 PRIMARY OUTCOME MEASURE:

- True positive rate (TPR): The electrical stimulation will be applied at 10% below threshold, i.e., at 90% sensory threshold for 30 times. The number of times the participant correctly identifies the stimuli will be scored out of total 30 number of trials (Bottini et al., 2013; Ferre et al., 2012; Ferrè et al., 2011; Ferre et al., 2013).

5.5 SECONDARY OUTCOME MEASURES:

- True negative rate (specificity): This will be the number of trials in which the participants received a catch (i.e., no stimulation), and said "NO". (Ferre et al., 2011).
- False positive rates: This will be the number of trials in which the participants received a catch and said, "YES".
- False negative rate: This will be the number of trials in which 110% stimulus is given and participants say 'no'.
- Perceptual sensitivity (d')
- Response bias (C)

[figure not shown]
Signal detection analysis (Macmillan et al, 1991) will be used to interpret the data for the SSDT task. That is a reason for the plan to measure three categories (as described above) according to the participant's responses.

- COP sway length will be obtained from VALD Performance Force decks dual force plate system.

5. Methodology

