6.2 PROCEDURE

6.2.1 SET UP

The set-up is predetermined prior the start of data collection.

The nGVS machine, electrical stimulator, and associated leads/electrodes will be set up as below:

nGVS through 1X1 Galvanic vestibular stimulator

- Parameters set for the noisy galvanic stimulation (subthreshold)@ Waveform: Random Noise; Intensity: 1 mA, Polarity: Bipolar; Durations: 20 minutes.

Electrical stimulation through Digitimer DS7A

- Parameters set for the electrical stimulation; Voltage: 400(Vmax); Pulse width: 2000 us(microseconds) (I have chosen 2000 microseconds because it is 2 milliseconds, and 2 milliseconds is indeed 0.002 second which is bigger in turning the trigger and is not faint than the 500 microsecond). Also 500us is really brief pinprick and fires of the nerve; Intensity: as per staircase procedure.

Force plates

COP sway length was measured for 30 s twice at three timepoints: baseline, during intervention (+5 min) and post intervention (+ 5 min), at 100 Hz, in standing by VALD Performance Force decks dual force plate system. The average COP sway length value will be calculated.

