Further, a mixed between within subjects' analysis of variance (ANOVA) will be conducted to assess the impact of two different interventions (nGVS and sham) on the participant's scores of perceptual sensitivity d' and response bias (C) across three timepoints (Pre intervention, during intervention and post intervention). The normative check will be conducted using distribution before proceeding for ANOVA. A longitudinal analysis of covariance will be conducted to evaluate the primary null hypothesis that the true positive rate is equal across the two conditions. For this purpose, a linear mixed regression model will be constructed. The model will be estimated post-intervention outcomes while adjusting for the pre-intervention outcomes. To account for repeat measures from the same participants, the model estimation will be done as a participant-wise random intercept. The null hypothesis will be tested by statistically comparing the model-estimated post-intervention means using t-tests. The statistical significance level will be set at 0.05. These means and their differences will be reported along with their 95% confidence intervals

A statistical analysis will be carried out using SPSS software. Data from each outcome measure will be analysed using two-way repeated measures ANOVA and post hoc t-tests to explore main effects and interactions.

The mean difference of Sway path length parameter will be analysed.

12. Quality Assurance

The research assistant will be trained in the protocol (if required) by [name].

13. Recruitment

If all participants have not been recruited by six months, recruitment will be ceased, and data collection/analysis will continue with those already recruited.

14. Project Management

[name]	Responsible for overall management of the research including organising appointment and supervision of RAs, recruitment, scheduling sessions, data collection, data processing, and data analysis.
Research Assistant	Responsible for assisting with data collection in lab sessions and doing randomisation and delivering the interventions or control as required.
[name]	Supervising project (primary supervisor).
[name]	Supervising project (secondary supervisor). Overseeing data collection processes.
[name]	Supervising project (Advisor).

15. Screening

The Researcher will screen all potential participants using a screening form.

Forms attached separately.

16. Informed Consent

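### Secondary objective 2 asks whether change in perception alters sway, but every sway analysis named in the protocol compares sway means without a perception variable

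*Protocol*

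**What the plan says.** The summary table at the front of the Protocol (Aims and Objectives) gives the second secondary objective as: "To determine whether change in sensory perception alters COP sway length during dual task paradigm". The background text before Section 3 repeats it, and research question 3 in Section 3 asks: "Does the change in sensory perception alters the COP sway length (total excursion) in healthy older adults during dual task paradigm". The rationale has the same direction: "this study will assess if the change in somatosensory perception could have impact on balance outcomes".

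Section 11 (Statistical analysis) holds two statements that reach sway:

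- One is specific to it: "The mean difference of Sway path length parameter will be analysed". It does not say whether the difference is between conditions, between timepoints or in change from baseline.
- One is general: "Data from each outcome measure will be analysed using two-way repeated measures ANOVA and post hoc t-tests to explore main effects and interactions". Section 5.5 lists sway among the secondary outcomes ("COP sway length will be obtained from VALD Performance Force decks dual force plate system"), so this sentence covers it.

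The other models in Section 11 are for other outcomes. The mixed model is tied to the true positive rate (TPR): "A longitudinal analysis of covariance will be conducted to evaluate the primary null hypothesis that the true positive rate is equal across the two conditions". The mixed between-within ANOVA is for d' and response bias C.

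**The concern.** The objective names change in perception as the explanatory variable and sway as the response. The stated analyses take condition and time as explanatory variables and leave perception out. These are different estimands. Stimulation could shift mean sway with no link to perception. Participants whose perception changes most could also be those whose sway changes most, with no shift in mean sway at all.

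If Section 11 is followed as written, secondary objective 2 has no analysis that answers it. The word *alters* raises a second difficulty. Participants are randomised to the order of nGVS and sham, not to a change in perception, so even a well-chosen analysis of the link would support an association and not a causal statement.

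**Working it through.** **Objective against analysis**

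| Place in Protocol | Response | Explanatory variable | Perception term for sway? |
|---|---|---|---|
| Objective 2, research question 3 | Sway | Change in perception | Required |
| Section 11, sway sentence | Sway | Not named | No |
| Section 11, two-way ANOVA for each outcome | Sway, among others | Read here as condition and time | No |
| Section 11, mixed model | TPR | Condition, adjusted for pre-intervention value | Not about sway |
| Section 11, between-within ANOVA | d' and C | Intervention and timepoint | Not about sway |

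No correlation, regression, covariate or mediation analysis relates perception to sway anywhere in the document. The wording of the objective is not a slip for a condition effect: the primary aim and the first secondary objective both spell out nGVS compared with sham, and the second secondary objective does not.

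**Does a test of mean sway respond to the link?**

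Let P be a participant's change in perception and S the change in sway. A mean-difference analysis estimates E[S]. The objective concerns Cov(P, S)/Var(P). Neither determines the other.

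This was checked by simulation with 20,000 runs of n = 27, where S = m + r·p + √(1 − r²)·e, with p and e independent standard normal and P = 0.5 + p. The values of m and r are assumptions, since the Protocol gives none. Tests were two-sided at 5%. The 0.05 level is in Section 11 and two-sidedness is assumed.

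| Mean sway shift m (SD) | True correlation r | Mean-difference test rejects | Association test rejects |
|---|---|---|---|
| 0 | 0 | 5.1% | 4.9% |
| 0 | 0.6 | 4.9% | 93% |
| 0.6 | 0 | 85% | 5.3% |
| 0.6 | 0.6 | 85% | 93% |

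The mean-difference test follows m and ignores r. The association test does the reverse.

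**Scale of an association test**

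Section 10 gives 27 participants without an effect size, SD or power, so that number cannot be reproduced and the point does not depend on it. With one (P, S) pair per participant and all 27 recruited, Fisher's z gives:

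- 80% power: tanh((1.960 + 0.842)/√(27 − 3)) = tanh(2.802/4.899) = tanh(0.572) = 0.52
- 90% power: tanh((1.960 + 1.282)/4.899) = tanh(0.662) = 0.58

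From Φ(atanh(r)·√24 − 1.960), power is about 7% at r = 0.1, 33% at r = 0.3 and 77% at r = 0.5 (assumed values of r).

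**Can the two changes be paired?**

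The detection task is given before, during and after each intervention (Section 6.2.4), and sway is recorded at baseline, during and post (Section 6.2.1), so changes in both can be formed. The timing of sway is not consistent, however. The Method part of the summary table places the recording during stimulation in the first 5 minutes, Section 6.2.1 gives +5 min, and Section 6.2.5.1 gives the last 2 minutes of sensory testing. One run of the task takes 70 × 13 s = 910 s, about 15 minutes. The two sway recordings with their gap take 30 + 5 + 30 = 65 s, the time of 65/13 = 5 trials. Which perception score belongs with which sway reading therefore has to be settled first.

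**The case against.** The strongest reply is that a protocol may leave the model for a secondary objective to a statistical analysis plan, which may exist here. That would carry weight if Section 11 were silent on sway or deferred the matter. It does neither: it names its sway analyses, and they address a different question. The mismatch lies within this one document.

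Several stronger readings are tempting, and the Protocol does not support them:

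- A reader might infer that the mean difference is the only sway analysis. The two-way ANOVA covers sway as well. It has no perception term either, so the mismatch remains.
- A reader might take the mean difference to be nGVS versus sham. That is plausible, but Section 11 does not say so.
- A reader might conclude that the trial will present a sway comparison as the answer to research question 3. Nothing in the Protocol says this. What can be said is that no stated analysis answers that question.
- A reader might treat 0.52 as the smallest correlation that a repeated-measures analysis here could detect. It is not. Such a model could use up to four sway outcomes per participant (during and post, in two sessions), and its power depends on within-participant correlations that the Protocol does not give. Section 13 also closes recruitment at six months with whoever has been enrolled, so 27 is not assured.

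It is also fair to say that this is the second of two secondary objectives, that the primary TPR model is untouched, and that rewording the objective would close the gap without any new analysis.

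**Conclusion.** The point holds in this form: secondary objective 2 and research question 3 cannot be answered by the sway analyses that Section 11 states, because those compare means and carry no perception variable. This rests on the text alone and on no numerical assumption. The simulation illustrates it under assumed effects, and the detectable |r| of about 0.52 indicates scale only, for one pair per participant, full recruitment, two-sided 5% and 80% power. It supports calling any association analysis exploratory. The change should be made, but it does not bear on the primary result.

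**What to change.** 1. State the randomised sway question explicitly: *Does nGVS versus sham alter COP sway length?* Analyse it with a mixed model of the kind Section 11 gives for TPR, with pre-stimulation sway from the same session as covariate, a random participant intercept and a term for period. Name the contrast and the timepoints in place of the unspecified mean difference.
2. For the perception-to-sway question, do one of two things:
   - drop that wording from objective 2, research question 3 and the rationale; or
   - add an analysis, labelled exploratory and associational, of change in TPR (or in d' from the 90% trials) against change in sway at the matching timepoint. Split the perception change into the participant's mean and the deviation from it, because raw change in a random-intercept model mixes between- and within-participant association. State that, with condition in the model, the coefficient is the association given condition and so leaves out the mean change in perception that nGVS itself produces. Replace *alters* with *is associated with*.
3. If the association is kept, reconcile the sway timing in the Method part of the summary table, Section 6.2.1 and Section 6.2.5.1, and say which perception score pairs with which sway reading.

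The cost is a few sentences in the objectives, Section 3 and Section 11, plus one decision on timing to be carried through the three places. No measurement is added, since both outcomes are already planned before, during and after each session.
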